8.2.3.4. Exploratory analyses

Additional analyses may be performed as necessary. Exploratory analyses will be reported only if results provide important interpretation.

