3. INTERIM AND FINAL ANALYSES

In this study, an interim analysis will be performed at the time of preparation of the report at 6 months after the start of the study or when the number of study patients exceeds 1000, whichever comes first. In addition, interim analyses for periodic safety reports will be performed periodically. For an interim analysis, only necessary items selected from the full analysis items defined in this Statistical Analysis Plan will be analyzed. A final analysis will be conducted to support the application of reexamination. For the final analysis, the full items defined in this Statistical Analysis Plan will be analyzed.

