4. HYPOTHESES AND DECISION RULES

Since this study is not a confirmatory study, the test will be positioned as an exploratory one.

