4.1. Statistical Hypotheses

The p-value of the test result will be evaluated as descriptive statistics and the significance level will not be specified, but a threshold may be set post-hoc for the purpose of screening.

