8.2.4.8. Exploratory analyses

For Efficacy Analysis Set 1, changes over time in viral load, body temperature, and percutaneous arterial oxygen saturation (SpO₂) in individual patients will be superimposed on the figures. For measured values before the start of treatment with this drug (including the start date of treatment), the last measured value before the start of treatment with this drug will be shown based on the handling of each endpoint in Section 6.3.

Additional analyses may be performed as necessary. Exploratory analyses will be reported only if results provide important interpretation.

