9. LISTINGS

The following listings will be prepared:

- Patient listing
- List of patients with adverse events
- List of patients with adverse reactions
- List of patients with adverse reactions excluded from safety analysis
- List of patients with excluded adverse reactions included in safety analysis
- List of patients with adverse reactions among contraindicated patients
- List of patients with serious adverse reactions

- List of patients with serious adverse events
- List of deaths
- List of efficacy evaluation
- List of complications corresponding to risk factors for aggravation of infection caused by SARS-CoV-
- List of concomitant drug therapies for infection caused by SARS-CoV-2
- List of concomitant non-drug therapies for infection caused by SARS-CoV-2
- List of SARS-CoV-2 viral tests
- List of body temperature and percutaneous arterial oxygen saturation (SpO₂)

In addition, forms necessary for re-examination application (PSEHB/PED Notification No. 0325-10 dated March 25, 2020 issued by the Director of Pharmaceutical Evaluation Division, Pharmaceutical Safety and Environmental Health Bureau, Ministry of Health, Labour and Welfare) will be prepared.

Furthermore, forms necessary for periodic safety reports (PSEHB/PED Notification No. 1128-5 dated November 28, 2017 issued jointly by the Director of Pharmaceutical Evaluation Division and the Director of Pharmaceutical Safety Division, Pharmaceutical Safety and Environmental Health Bureau, Ministry of Health, Labour and Welfare) will be prepared.

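### SAP 8.2.3.4 and 8.2.4.8 make the reporting of an open-ended set of exploratory analyses depend on their results, and leave unclear whether the planned overlay figures are covered

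*SAP*

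**What the plan says.** SAP 8.2.3.4 consists of two sentences. The first opens the set: "Additional analyses may be performed as necessary". The second filters it: "Exploratory analyses will be reported only if results provide important interpretation". SAP 8.2.4.8 repeats both word for word. Neither section says what makes a result important, who decides, when, or whether a record is kept of analyses run but not reported.

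In 8.2.4.8 the pair follows a paragraph that plans specific output. It calls for individual-patient overlay plots in Efficacy Analysis Set 1 of "changes over time in viral load, body temperature, and percutaneous arterial oxygen saturation". The section heading is Exploratory analyses, and the figures are not expressly exempted from the filter.

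Four other places bear on the point:

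- SAP 4: "Since this study is not a confirmatory study, the test will be positioned as an exploratory one".
- SAP 4.1: p-values are descriptive, and "the significance level will not be specified, but a threshold may be set post-hoc for the purpose of screening".
- SAP 3: "For the final analysis, the full items defined in this Statistical Analysis Plan will be analyzed".
- SAP 9: the listings include "List of SARS-CoV-2 viral tests" and a listing of body temperature and SpO2, both without condition.

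**The concern.** The filter is a stated rule, not an omission. An analyst who follows it exactly runs additional analyses, looks at the results, and leaves out those judged unimportant. Unremarkable results are the natural candidates for omission, so the reported subset is expected to lean toward larger effects. A reader who sees one striking result cannot tell whether it was one of one or one of forty.

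This matters more here because no significance level is fixed and a screening threshold may be chosen afterwards. The number of analyses performed is then the reader's main guide to how easily chance could have produced a finding. Protocol 8.9 acknowledges that there is no control group to help separate a chance signal from a real one. The results support the re-examination application (SAP 3), may be published (Protocol 11), and are considered when the risk management plan is reviewed (Protocol 13).

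A second, smaller issue is that the planned overlay figures share the section with the filter. One reading lets them be omitted according to how they look.

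**Working it through.** **1. The plan's own figures.** The documents attach no number to the reporting rule. The inputs borrowed for the illustration are the 3000 patients and the 7.8% adverse reaction rate in Protocol 8.5, and the related statements there hold up:

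- At least one case at a frequency of 0.1%: 1 − (1 − 0.001)^3000 = 0.950. The exact requirement is ln(0.05)/ln(0.999) = 2994.2, so 2995. The plan's 3000 is consistent.
- At least 214 patients with reactions: for a binomial with n = 3000 and p = 0.078, P(X ≥ 214) = 0.920, which meets the stated 90%.

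**2. Which analyses carry the rule.** Reading the SAP section by section:

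| Sections | Filtered on results? |
|---|---|
| 8.2.3.1 to 8.2.3.3 (adverse reactions, adverse events, safety subgroups) | No |
| 8.2.4.1 to 8.2.4.7 (severity, symptoms, death, hospitalization, efficacy subgroups) | No |
| 8.2.3.4 and 8.2.4.8, additional analyses | Yes |
| 8.2.4.8, overlay figures | Unclear |
| 9, listings of viral tests, temperature and SpO2 | No |

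**3. Illustration of the tilt.** Assumptions, none of them from the SAP: an additional analysis compares 300 with 2700 patients on adverse reactions; the comparison group has the 7.8% rate; a result counts as important if the 95% Wald interval for the risk ratio excludes 1.

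By hand, for a true ratio of 1.2:

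- Rates are 0.078 and 1.2 × 0.078 = 0.0936. Expected counts are 2700 × 0.078 = 210.6 and 300 × 0.0936 = 28.1.
- SE of the log ratio = √[(1 − 0.0936)/28.08 + (1 − 0.078)/210.6] = 0.191.
- The interval lies above 1 only if the estimate exceeds about exp(1.96 × 0.191) = 1.46. An estimate near the true 1.2 cannot pass, so whatever passes is too large.

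Simulation with 400,000 pairs of binomial counts per setting:

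| Sizes | True ratio | Reported as raised | Median ratio when raised |
|---|---|---|---|
| 300 vs 2700 | 1.0 | 3.0% | 1.50 |
| 300 vs 2700 | 1.2 | 17.4% | 1.53 |
| 300 vs 2700 | 2.0 | 98% | 2.00 |
| 100 vs 2900 | 1.2 | 10.9% | 1.85 |

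For 300 vs 2700 with no true effect, a further 1.8% are reported as lowered, at a median of 0.55, so about 4.8% are reported in all. For a true ratio of 1.2, the nominal 95% interval covers the truth in about 83% of the raised results at 300 vs 2700, and in about 69% at 100 vs 2900. Without the filter, the median ratio at 300 vs 2700 is 1.19. The exaggeration is large for null or small effects and absent for a large, well-powered one.

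**4. Illustration of the hidden count.** With k independent null analyses and a 5% filter, the chance of at least one reportable result is 1 − 0.95^k: 0.64 for k = 20 and 0.87 for k = 40. Analyses of the same patients are usually correlated, so these are not predictions for this study.

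**5. The overlay figures.** They show individual patients and give no effect estimate, so step 3 does not apply to them. The only question is whether they may be left out.

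**The case against.** The strongest reply is that the criterion is interpretive importance, not size or significance. A reassuring null result could qualify, so a reader who infers that reported effects *are* exaggerated, or by how much, goes beyond the text. That stands: exaggeration is a likely tendency, and its size depends on how the rule is applied.

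A second reply is that the illustration uses adverse reaction risk ratios by subgroup, a type of analysis that 8.2.3.3 already plans without a results filter. That also stands. Only further, unplanned comparisons fall under 8.2.3.4, and the main conclusions of the study are not exposed. Nor does the SAP forbid a count of the analyses performed; it is silent on one.

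A reader might also infer from 8.2.4.8 that the planned figures may be dropped if unfavourable, and that the course of viral load and vital signs would then vanish. The documents do not support this. The figures are worded as definite output, the filter stands in a separate paragraph after the sentence on additional analyses, SAP 3 commits to analysing every SAP item at the final analysis, and Section 9 lists the underlying data. What remains is an ambiguity: the heading covers the figures, and SAP 3 speaks of analysing, not of reporting.

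The last reply is that every test here is exploratory anyway. This does not answer the point. With no fixed significance level, disclosure of what was run matters more.

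**Conclusion.** The concern holds in a limited form. The SAP states, in two places, a rule that makes the reporting of an unspecified set of analyses depend on their results. It hides the number of analyses run and is likely to tilt those reported toward larger effects. The prespecified safety, efficacy and subgroup analyses are unaffected. The documents do not allow the size to be computed. The figures of about 17% and a median ratio of 1.53 for a true 1.2 rest on the assumed interval filter, the assumed group sizes and the protocol's 7.8% rate. For the overlay figures, the finding is only that the text leaves their reporting unclear. The point is modest in weight and cheap to settle.

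**What to change.** In SAP 8.2.3.4 and 8.2.4.8, replace the conditional sentence with:

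> *All additional exploratory analyses performed will be listed in the report or an appendix with a brief result, whatever the result, and identified as not pre-specified.*

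In 8.2.4.8, add that the planned overlay figures of viral load, body temperature and SpO2 are always produced and reported. A one-line entry per additional analysis is enough; full output for each is not needed.

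The cost is a wording change in two sections, a short appendix table and a slightly longer report. No new data or patients are needed, and no stated figure in the plan changes.

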8.2.4. Efficacy analyses

Refer to Section 6.2 for the efficacy evaluation period. Sensitivity analysis will be performed by changing the evaluation period based on the end date of the observation period to the secondary definition described in Section 6.2 but not for subgroup analyses and exploratory analyses.

8.2.4.1. Worsening of severity and highest severity of infection caused by SARS-CoV-2

The following analyses will be performed in Efficacy Analysis Sets 1, 2, and 3.

For worsening of severity of infection caused by SARS-CoV-2, the frequency and proportion of each category will be calculated. The confidence interval of the proportion will also be calculated for "worsened."

For the highest severity, the frequency and proportion of each category will be calculated. The denominator of the proportion will be the number of patients with worsening. For the highest severity (moderate II or severe), the frequency and proportion of moderate II or severe and its breakdown (moderate II, severe, moderate II or severe [indistinguishable]), and the confidence interval will be calculated.

8.2.4.2. Presence or absence and severity of symptoms as of the end date of the observation period

In Efficacy Analysis Sets 1, 2, and 3, the frequency and proportion of each category will be calculated. The breakdown of "symptoms present" will also be tabulated.

8.2.4.3. Resolution of symptoms and improvement in severity from the start of treatment with this drug as of the end date of the observation period

The following analyses will be performed in Efficacy Analysis Sets 1, 2, and 3.

For resolution of symptoms from the start of treatment with this drug as of the end date of the observation period, the frequency and proportion of each category will be calculated. For "resolved," the confidence interval of the proportion will also be calculated.

For the improvement in severity from the start of treatment with this drug as of the end date of the observation period, the frequency and proportion of each category will be calculated. For "improved," the confidence interval of the proportion will also be calculated.

8.2.4.4. Resolution of symptoms and improvement in severity after worsening of severity during the observation period as of the end date of the observation period

Among the patients in Efficacy Analysis Sets 1, 2, and 3, the following analyses will be performed in those who showed worsening of the severity of infection caused by SARS-CoV-2 after the start of treatment with this drug (patients with worsening).

The frequency and proportion of each category will be calculated for resolution of symptoms after worsening of severity during the observation period as of the end date of the observation period. For "resolved," the confidence interval of the proportion will also be calculated.

For the improvement in severity after worsening during the observation period as of the end date of the observation period, the frequency and proportion of each category will be calculated. For "improved," the confidence interval of the proportion will also be calculated.

8.2.4.5. Death from any cause

Deaths from any cause will be analyzed in Efficacy Analysis Sets 1, 2, and 3 as described in Section 8.1.4.

The frequency and proportion of events and censoring will be calculated separately. The period at risk of events is defined as the number of days from the start date of treatment to the onset date of event, date of last observation, or Day 28 after the end of treatment, whichever comes first, and the mean will be calculated.

For the number of days from the start date of treatment to the onset date of event, frequency and its proportion will be calculated and shown in a figure.

8.2.4.6. Hospitalization for treatment of infection caused by SARS-CoV-2 or death from any cause

Hospitalization for treatment of infection caused by SARS-CoV-2 or death from any cause will be analyzed in Efficacy Analysis Sets 2 and 3 in accordance with Section 8.1.4.

The frequency and proportion of events and censoring will be calculated separately. Events will be tabulated not only for hospitalization or death but also for each. The period at risk of events is defined as the number of days from the start date of treatment to the onset date of event, date of last observation, or Day 28 after the end of treatment, whichever comes first, and the mean will be calculated.

For the number of days from the start date of treatment to the onset date of event, frequency and its proportion will be calculated and shown in a figure.

For patients who developed events, the following patient characteristics will be tabulated according to Section 8.1.

- Age
- Number of risk factors for aggravation of infection caused by SARS-CoV-2 [absent, 1, 2, 3, 4, number unknown, unknown] * If the number of applicable risk factors is unknown, "number unknown" should be selected. If it is not known that there are risk factors, the patient will be classified as "unknown."
- Number of SARS-CoV-2 vaccination doses (vaccination on or before the day before the start of administration of this drug) [none, 1, 2, 3, 4 or more, unknown]

As a sensitivity analysis, the above analysis will be performed by changing the definition to the event definition of hospitalization shown in Section 6.2.

8.2.4.7. Subgroup analyses

Subgroup analyses of the following efficacy endpoints will be performed based on Section 8.1 by factor specified in Section 5.4. However, if there is a category with less than 10 patients and it is determined difficult after reconsideration of the classification of categories, the ratio for the category will not be calculated. The analysis sets to be analyzed are specified in Section 5.4.

• Worsening of severity: The risk ratio of "worsened" and the 95% confidence interval will be estimated.

- Resolution of symptoms: The risk ratio of "resolved" and the 95% confidence interval will be estimated (only for the entire period). * Excluding the factor "symptoms and severity of infection caused by SARS-CoV-2 at the start of treatment with this drug"
- Improvement in severity: The risk ratio of "improved" and the 95% confidence interval will be estimated (only for the entire period). * Excluding the factor "symptoms and severity of infection caused by SARS-CoV-2 at the start of treatment with this drug"
- Death from any cause: The hazard ratio of events from the start of treatment with this drug to Day 28 and the 95% confidence interval will be estimated.
- Hospitalization or death from any cause: The hazard ratio of events from the start of treatment with this drug to Day 28 and the 95% confidence interval will be estimated.
- Hospitalization or death from any cause (sensitivity analysis): The hazard ratio of events from the start of treatment with this drug to Day 28 and the 95% confidence interval will be estimated.

8.2.4.8. Exploratory analyses

For Efficacy Analysis Set 1, changes over time in viral load, body temperature, and percutaneous arterial oxygen saturation (SpO₂) in individual patients will be superimposed on the figures. For measured values before the start of treatment with this drug (including the start date of treatment), the last measured value before the start of treatment with this drug will be shown based on the handling of each endpoint in Section 6.3.

Additional analyses may be performed as necessary. Exploratory analyses will be reported only if results provide important interpretation.

9. LISTINGS

The following listings will be prepared:

- Patient listing
- List of patients with adverse events
- List of patients with adverse reactions
- List of patients with adverse reactions excluded from safety analysis
- List of patients with excluded adverse reactions included in safety analysis
- List of patients with adverse reactions among contraindicated patients
- List of patients with serious adverse reactions

- List of patients with serious adverse events
- List of deaths
- List of efficacy evaluation
- List of complications corresponding to risk factors for aggravation of infection caused by SARS-CoV-
- List of concomitant drug therapies for infection caused by SARS-CoV-2
- List of concomitant non-drug therapies for infection caused by SARS-CoV-2
- List of SARS-CoV-2 viral tests
- List of body temperature and percutaneous arterial oxygen saturation (SpO₂)

In addition, forms necessary for re-examination application (PSEHB/PED Notification No. 0325-10 dated March 25, 2020 issued by the Director of Pharmaceutical Evaluation Division, Pharmaceutical Safety and Environmental Health Bureau, Ministry of Health, Labour and Welfare) will be prepared.

Furthermore, forms necessary for periodic safety reports (PSEHB/PED Notification No. 1128-5 dated November 28, 2017 issued jointly by the Director of Pharmaceutical Evaluation Division and the Director of Pharmaceutical Safety Division, Pharmaceutical Safety and Environmental Health Bureau, Ministry of Health, Labour and Welfare) will be prepared.

10. APPENDICES

10.1. Appendix 1: Handling of Efficacy-related Questionnaire Items in the Identification of Efficacy Analysis Sets

Table 1. Identification of Efficacy Analysis Sets 1 and 2

Case	Stat	Status of CRF entry		Safety Analysis Set‡	Efficacy	Efficacy Analysis Set 1†‡		Efficacy Analysis Set 2†‡			
	Adverse	Hospitali	Efficacy	Inclusion/	Inclusion/	Eval	uable	Inclusion/		Evaluable	
	event page	zation status page	evaluatio n page	exclusion (Reason)	exclusion (Reason)	Deaths	Severity related	exclusion (Reason)	Deaths	Hospitalization or death	Severity related
1	Yes	Yes	Yes	Included	Included	Yes	Yes	Included	Yes	Yes	Yes
2	No	Yes	Yes	Excluded (AE information)	Included	Unknown	Yes	Included	Unknown	Yes (only hospitalization events present) or unknown	Yes
3	Yes	No	Yes	Included	Included	Yes	Yes	Included	Yes	Yes (only death events present) or unknown	Yes
4	Yes	Yes	No	Included	Included	Yes	Unknown	Included	Yes	Yes	Unknown
5	No	No	Yes	Excluded (AE information)	Included	Unknown	Yes	Included	Unknown	Unknown	Yes
6	No	Yes	No	Excluded (AE information)	Included	Unknown	Unknown	Included	Unknown	Yes (only hospitalization events present) or unknown	Unknown
7	Yes	No	No	Included	Included	Yes	Unknown	Included	Yes	Yes (only death events present) or unknown	Unknown
8	No	No	No	Excluded (AE information)	Excluded (Efficacy information)	NA	NA	Excluded (Efficacy Set 1)	NA	NA	NA

AE, adverse event; NA, not evaluated due to exclusion from population

[‡] For the CRF pages to be used to identify the population other than the adverse event page, hospitalization status page, and efficacy evaluation page, it is assumed that there are no items meeting the exclusion criteria.

10.2. Appendix 2: Data Extraction Details

 Table 2.
 Definitions of Acceptable Windows for Timing

Timing	Endpoint	Definition [acceptable window]
At the start of treatment	Efficacy endpoints, viral load, body temperature, percutaneous arterial oxygen saturation	From 30 days prior to the date of first dose in this study (start date of treatment) to the start date of treatment
During the observation period	Safety endpoints, efficacy endpoints, viral load, body temperature, percutaneous arterial oxygen saturation, concomitant drug therapy, and non-drug therapy	Start date of treatment to Day 28 after the end of treatment
End date of the observation	Efficacy endpoints	Primary definition: Up to Day 28 after the end of treatment
period		Secondary definition 1: Up to 42 days after the end of treatment
		Secondary definition 2: Entire period

10.3. Appendix 3: Data Entries Related to Efficacy Endpoints and Their Handling, and Assessment of Endpoints

Table 3. Worsening of Severity and Highest Severity of Infection Caused by SARS-CoV-2

Symptoms	Severity at			Worsening of	of severity: H	ighest sev	erity			
at the start of	the start of treatment	Worsening	Vorsening of severity during the observation period							
treatment	with this	Absent		Present						
with this	drug	Highest seve	erity	ity						
drug		NA	Mild	Moderate I	Moderate II	Severe	Unknown	NA		
Absent	NA	Absent: NA	Present: Mild	Present: Moderate I	Present: Moderate II	Present: Severe	Present: Unknown	Unknown: NA		
Present	Mild		Case 1				Case 2			
	Moderate I									
	Moderate II									
	Severe	Severe at the start: NA	Case 3							
	Unknown	Absent: NA	Case 4							
Unknown	NA	Case 5								

NA: not applicable

Discrepancies between evaluations at the start of treatment with this drug and during the observation period are subject to re-investigation, but the reasons for being subject to re-investigation and handling of cases where there is no change as a result of re-investigation are shown below.

- Case 1: Assessed as "Unknown: NA" because the highest severity is lower than the severity at the start of treatment with this drug.
- Case 2: Assessed as "Unknown: NA" because the severity during the observation period is unknown. However, if the severity is considered to have worsened during the observation period, it will be handled as "Present: Unknown" for analysis. In addition, when the severity at the start is moderate I, the highest severity will be considered as "moderate II or severe (indistinguishable)" for analysis, and when the severity at the start is moderate II, the highest severity will be considered as "Present: Severe" for analysis.
- Case 3: Assessed as "Unknown: NA" because the severity is severe at the start but worsened during the observation period. However, if the severity is assessed as severe at the start, worsening of severity will be handled as "sever at the start" and the highest severity will be handled as NA.
- Case 4: Assessed as "Unknown: NA" because the severity at the start is unknown. However, if the severity is judged to have worsened during the observation period, worsening of severity will be handled as "present" and the highest severity entered will be the highest severity for analysis.
- Case 5: Assessed as "Unknown: NA" because the symptoms at the start are unknown.

Table 4. Resolution of symptoms from the start of treatment with this drug as of the end date of the observation period

Symptoms at the	Resolu	ition of symp	toms						
start of treatment	Symptoms at the end of the								
with this drug	observation period								
	Absent	Absent Present Unknown							
Absent	No								
	symptoms at								
	the start of								
	treatment	t Absent Unknown							
	with this								
	drug								
Present	Present								
Unknown	Unknown								

Table 5. Improvement in severity from the start of treatment with this drug as of the end date of the observation period

Symptoms	Severity at	Improvement in severity								
at the start	the start of	Symptoms a	Symptoms at the end date of the observation period							
of	treatment	Absent	Absent Present							
treatment	with this	Severity at t	the end da	te of the ob	servation p	eriod				
with this	drug	NA	Mild	Moderate	Moderate	Severe	Unknown	NA		
drug				I	II					
Absent	NA	No symptom	ns at the sta	art of treatme	ent with this	drug				
Present	Mild	Present	Absent							
	Moderate I									
	Moderate									
	П									
	Severe									
	Unknown									
Unknown	NA	Unknown	•				•
